12.5.1.3 Data Transformation

In the case that the statistical assumptions for the ANOVA model are shown to be violated via the diagnostic tests then the primary efficacy parameter will be log-transformed. The ANOVA will then be re-run and checked via the diagnostic tests. If the ANOVA assumptions now hold this will be used. If they do not hold then the alternative method shall be used on the non-log-transformed data.

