## 10.5 Primary Efficacy Analysis

The primary endpoint / efficacy variable is the intra-operative blood loss after decision to treat the subject with IMP until the end of surgery as measured and calculated by amount of blood from the blood suction unit and amount of blood from surgical cloths and compresses.

The primary analysis of this endpoint will test for non-inferiority in the PPS.

The null hypothesis for the primary analysis is that the degree of inferiority of BT524 compared to standard treatment (FFP/cryoprecipitate) is greater than or equal to the non-inferiority margin. The alternative hypothesis is that the degree of inferiority of BT524 compared to FFP/cryoprecipitate is less than the non-inferiority margin.

 $H_0: µ_1 - µ_2 ≥ δ$  $H_1: µ_1 - µ_2 < δ$ 

where

- µ1 = mean intra-operative blood loss after the decision to treat the subject with IMP in the BT524 treatment arm
- µ2 = mean intra-operative blood loss after the decision to treat the subject with IMP in the FFP-/cryoprecipitate-treatment arm
- $\delta$  = non-inferiority margin = 150 mL

The final analysis will be performed using ANCOVA with the intra-operative blood loss after the decision to treat the subject with IMP until the end of surgery as the dependent variable and the predictive blood loss (>1,000 mL to  $\leq$  2,000 mL and > 2,000 mL) as a covariate. The least square means and treatment difference (BT524 versus standard treatment) in least square means will be presented with the corresponding 95% confidence intervals and 2-sided p-value. Non-inferiority will be demonstrated if the upper confidence limit of the 2-sided 95% confidence interval for the difference in the least square means is less than the non-inferiority margin (150 mL).

This analysis will also be performed in the FAS as a sensitivity analysis.

If non-inferiority is demonstrated, then superiority will be assessed in the FAS with superiority demonstrated if the 2-sided p-value is less than 0.05 (i.e., the upper confidence interval is less than 0 mL) using the analysis performed to assess Non-Inferiority.

No imputation for missing values will be applied.

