4.1 Changes from Protocol

An additional mFAS population has been defined to follow ICH guidance.

The full analysis set (FAS) as defined in section 10.1 in the protocol "The FAS comprises all subjects who received at least one dose of IMP prior to the 'end of surgery' and have at least one post dose efficacy assessment", has been altered in section 9.03 of this SAP version to "All randomized subjects receiving IMP post randomization and with data collected post randomization will be included in the FAS. Exclusion from the FAS can be considered in special cases as described in ICH E9, section 5.2.1.". In addition, the previous FAS definition stemming from the protocol and defined in Section 9.0 of SAP version 5.0 is renamed to modified FAS (mFAS). These changes are done to be compatible with ICH E9 section 5.2.1.

Additional steps have been added for the efficacy section to allow for the potential of non-normal data. These are data transformations and a non-parametric Van Elteren's method as specified in Section 12.5.1. This is an extension to Section 10.5 of the protocol.

Overall Mortality has been added to the SAP in Section 12.5.3.8 as a secondary efficacy endpoint.

Per Section 10.5 of the protocol, there will be no imputation of missing values. Imputation has since been deemed necessary from SAP version 2.0. These rules are now defined in Section 8.4.

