6.2 Sample Size Considerations

The non-inferiority margin is defined as 150 mL blood loss, as such difference in blood loss after the decision to treat the subjects with IMP is considered as clinically not relevant.

It is assumed that BT524 is non-inferior that means not worse than FFP/cryoprecipitate with a non-inferiority margin of 150 mL in reducing intra-operative blood loss. Assuming a blood loss of about 500 mL in the FFP/cryoprecipitate treatment arm after the decision to treat the subject with IMP until end of surgery, a standard deviation (SD) of 375 mL, a non-inferiority margin of 150 mL, an alpha-level of 2.5% (1-sided) 100 evaluable subjects per treatment arm are needed to demonstrate the non-inferiority of BT524 by using a t-test (equivalence) with 80% power.

Based on the results of the blinded sample size recalculation (see section 6.2.1) the power was reduced from 90% to 80% to allow an increase of the originally assumed SD of 325 mL to 375 mL.

The sample size will be recalculated at the interim analyses as defined in section 10.0. Sample size estimations will be performed using nQuery Advisor Version 4.0 or higher.

With 100 subjects per treatment arm superiority of BT524 can also be tested with a power of > 80% (t-test, alpha=0.05 2-sided, effect size Δ =0.5).

It is expected that approximately 10% of the randomized subjects will not fulfil the criteria to be included in the PPS. Therefore, approx. 220 randomized subjects are required to reach 200 evaluable subjects in the PPS.

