12.5 Efficacy Analyses

12.5.1 Primary Efficacy Parameter

The primary efficacy parameter is the intra-operative blood loss after decision to treat the subject with IMP until the end of surgery as measured and calculated by amount of blood from the blood suction unit and amount of blood from swabs, surgical cloths and compresses.

The primary objective of this study is to demonstrate that BT524 is non-inferior that means not worse than FFP/cryoprecipitate with a non-inferiority margin of 150 mL in reducing intra-operative blood loss by intravenous (IV) administration in subjects with acquired hypofibrinogenemia undergoing elective major spinal or abdominal surgery. The primary analysis of this endpoint is a non-inferiority test in the PPS. The null hypothesis for the primary analysis is that the degree of inferiority of BT524 compared to standard treatment (FFP/cryoprecipitate) is greater than or equal to the non-inferiority margin. The alternative hypothesis is that the degree of inferiority of BT524 compared to standard treatment.

where

- μ 1 = mean intra-operative blood loss after the decision to treat the subject with IMP in the BT524 treatment arm
- μ2 = mean intra-operative blood loss after the decision to treat the subject with IMP in the FFP/cryoprecipitate treatment arm
- δ = non-inferiority margin = 150 mL

The final analysis will be performed using a two-way analysis of variance (ANOVA) with the intra-operative blood loss after the decision to treat the subject with IMP until the end of surgery as the dependent variable

and the predictive blood loss (> 1,000 mL to \leq 2,000 mL and > 2,000 mL) as a covariate. The least square means and treatment difference (BT524 versus FFP/cryoprecipitate) will be presented with the corresponding 2-sided 95% confidence intervals and p-value. Non-inferiority will be demonstrated if the upper confidence limit of the 95% confidence interval for the difference in the least square means is less than the non-inferiority margin (150 mL). Assumptions for the ANOVA model will be evaluated by diagnostic (e.g., Shapiro-Wilk test for normality) and graphical methods such as residual plots, including distribution of residuals, and Q-Q plots of residuals. The ANOVA assumptions are reviewed during the BDRM and in case the assumptions are not fulfilled, data transformation and alternative methods are discussed (see sections 12.5.1.3 and 12.5.1.4).

In addition, the following analyses will be presented:

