12.5.1.1 Assessment of Superiority

If the non-inferiority is demonstrated by the primary analysis, then superiority will be assessed in the FAS and mFAS and repeated for surgery type, sex and race. For superiority analysis, the null hypothesis is that the blood loss in BT524 treatment arm is greater than that in FFP/cryoprecipitate treatment arm. The alternative hypothesis is that the blood loss in BT524 treatment arm is less than that in FFP/cryoprecipitate treatment arm.

H0: $\mu 1 - \mu 2 \ge 0$ H1: $\mu 1 - \mu 2 < 0$ where $\mu 1$ and $\mu 2$ are the same as above.

The same ANOVA model as the non-inferiority analysis will be used. The least square means and difference of least square means will be presented together with the 95% confidence intervals and 2-sided p-value. The superiority of BT524 is demonstrated if the 2-sided p-value is less than 0.05.

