12.5.1.4 Alternative Method

The statistical assumptions for the ANOVA model will be tested in regards to the primary endpoint. Primarily the outcome of a Shapiro-Wilk test and graphical quantile-quantile (QQ) plots will used to assess if the

assumptions are significantly violated. If deemed necessary other test may be performed as well. The methods used, and the conclusions will be discussed in the clinical trial report (CTR).

In case there is a significant violation to the assumptions for the ANOVA model for the primary endpoint, a non-parametric alternative method will be implemented, proposed by van Elteren for stratified or blocked continuous response variables.

This alternative method will be used as a sensitivity analysis to the primary non-inferiority analysis for the PPS, FAS and mFAS. It will also be used as a sensitivity to the superiority analysis for the FAS and mFAS.

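### The SAP's fallback steps for non-normal blood loss (log-transformed ANOVA, then van Elteren) define no test of the 150 mL margin, and the SAP contradicts itself on whether van Elteren decides

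*SAP*

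**What the plan says.** **Success rule.** SAP 6.2 fixes the margin on the mL scale: "The non-inferiority margin is defined as 150 mL blood loss". Protocol 10.5 gives the decision rule: "Non-inferiority will be demonstrated if the upper confidence limit of the 2-sided 95% confidence interval for the difference in the least square means" lies below that margin. SAP 12.5.1 repeats the rule for the per-protocol set. Neither document gives another rule.

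**Fallbacks.** The protocol has none. The SAP describes them in four places:

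- SAP 4.1: "Additional steps have been added for the efficacy section to allow for the potential of non-normal data". It presents them as extending Protocol 10.5.
- SAP 12.5.1: assumptions are reviewed at the blind data review meeting and, "in case the assumptions are not fulfilled, data transformation and alternative methods are discussed".
- SAP 12.5.1.3: if diagnostics show a violation, blood loss is log-transformed and the ANOVA re-run and re-checked. Then: "If the ANOVA assumptions now hold this will be used. If they do not hold then the alternative method shall be used", on untransformed data.
- SAP 12.5.1.4: the alternative is van Elteren's stratified rank test, called for directly on a significant violation with no mention of the log step. Its role: "This alternative method will be used as a sensitivity analysis to the primary non-inferiority analysis for the PPS, FAS and mFAS". It has the same role for superiority.

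**Superiority.** SAP 12.5.1.1: "The same ANOVA model as the non-inferiority analysis will be used".

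**The concern.** On the log path, the SAP directs an analysis that has no success criterion. The model compares geometric means as a ratio, while the hypothesis concerns a difference in arithmetic means of 150 mL. No ratio margin or back-transformation is given, and nothing labels the log ANOVA a sensitivity analysis.

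On the rank path, van Elteren as specified tests for no difference, so it cannot address a margin. SAP 12.5.1.3 and 12.5.1.4 also disagree on whether its result decides.

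A ratio margin, or a choice of deciding analysis, would then have to be settled at the blind data review. In a pivotal trial the decision rule should not be open at that stage. Superiority inherits the question of which model decides. It does not inherit the missing margin, because its null value is zero.

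**Working it through.** **Inputs from SAP 6.2:** margin 150 mL, control mean about 500 mL, SD 375 mL, one-sided level 2.5%, power 80%, 100 evaluable subjects per arm. **Assumed here:** true difference 0 for the sample size, and gamma or lognormal blood loss for the simulations.

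**1. The plan's own figure.** n per arm = 2 × (1.960 + 0.842)² × 375² / 150² = 98.1, rounded up to 99 by the normal approximation. The noncentral t gives 100 per arm with 80.4% power. The stated 100 is reproduced, as a test of a difference in arithmetic means in mL.

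**2. Is the trigger likely?** A normal variable with mean 500 and SD 375 would be negative with probability Φ(−500/375) = 9.1%. Blood loss cannot be negative, so right skew is expected. The SAP states no Shapiro-Wilk level; 5% is assumed. Rejection rates with 100 per arm:

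| Residuals | Gamma | Lognormal |
|---|---|---|
| Raw, one stratum (4,000 trials) | 100% | 100% |
| Log, one stratum | 97% | 5% |
| Raw, two strata (2,000 trials) | 100% | 100% |
| Log, two strata | 94% | 6% |

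The two strata have 60 and 40 subjects per arm, means of 400 and 650 mL and CV 0.7. In the single-stratum case, raw residuals were still rejected in 100% of trials at a 0.1% level. The log step is therefore likely to be reached; whether van Elteren follows depends on the distribution.

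**3. Does 150 mL translate to a ratio?** For a lognormal with these values the control geometric mean is 500/√(1 + 0.75²) = 400 mL. At a true mean difference of +150 mL the geometric-mean ratio is:

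- 1.30 if the effect is proportional, since 650/500 = 1.30;
- 1.44 if 150 mL is added to every value and the shape is lognormal;
- 1.52 if 150 mL is added to every value and the shape is gamma.

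Even for a proportional effect the ratio depends on the control mean: (m + 150)/m is 1.50 at 300 mL, 1.30 at 500 mL and 1.15 at 1,000 mL.

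**4. What does van Elteren test as specified?** With lognormal data, two equal strata and truly equal arms (8,000 trials), the unshifted test favoured BT524 in 2.4% of trials, which is the size of a test of no difference. The mL-scale rule declared non-inferiority in 81% of the same trials.

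**5. Is switching needed?** One-sided error at a true +150 mL, nominal 2.5% (40,000 trials for the mL-scale tests, 20,000 for the rank test, single stratum):

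| Test | Additive, gamma / lognormal | 1.3-fold, gamma / lognormal |
|---|---|---|
| mL scale, pooled t | 2.4% / 2.3% | 2.8% / 3.0% |
| mL scale, HC3 | 2.6% / 2.4% | 2.8% / 3.0% |
| Rank test with BT524 shifted by 150 mL | 2.6% / 2.5% | 12.9% / 17.3% |

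In the two-stratum lognormal simulation of step 4, the mL-scale rule had error 2.4% (additive) and 3.4% (1.3-fold), and the shifted van Elteren test 2.4% and 18.4%. The mL-scale test stays close to nominal despite marked skewness. A shifted rank test targets a location shift and does not protect the mean-difference hypothesis when the effect is proportional.

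**The case against.** The strongest reply is that the mL rule is complete and never revoked. SAP 12.5.1.4, the section that defines van Elteren, calls it a sensitivity analysis, which presupposes that the primary analysis stands. On that reading SAP 12.5.1.3 says when the method is run and 12.5.1.4 says in what role, so no 150 mL shift is needed. The added steps are described as an extension and are discussed under blinding, so a method could not be chosen on the treatment effect. The 100% trigger rate rests on assumed shapes and a mechanical test, whereas the SAP also uses QQ plots and judgement.

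Part of this stands. The charitable reading can remove the contradiction over van Elteren, and automatic switching is not certain. For superiority, both fallbacks give a valid test of no difference, though not of the mean difference stated in SAP 12.5.1.1. HC3 showed no advantage over the pooled test. The 13% to 18% error belongs to a shifted rank test that the SAP does not propose; it bears only on whether adding the shift would be an adequate repair.

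The reply does not reach the log step. The sensitivity label covers van Elteren alone, and the natural reading of 12.5.1.3 is that the log ANOVA replaces the untransformed model. Nowhere does the SAP say that the untransformed model still decides once its assumptions have failed. Blinding limits bias in choosing a method, but it does not supply a missing margin.

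**Conclusion.** The concern holds and should be corrected before database lock. Followed as written, SAP 12.5.1.3 leads, on a path that is likely to occur, to an analysis that cannot test the 150 mL hypothesis. SAP 12.5.1.3 and 12.5.1.4 also need to be reconciled on the role of van Elteren and on whether the log step comes first.

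The untransformed primary rule and the sample size are sound. The gap in the margin concerns non-inferiority; for superiority, what is unclear is which model decides.

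The missing margin and the conflict between sections follow from the text alone. The likelihood of the trigger, the ratios of 1.30 to 1.52 and the error rates rest on gamma or lognormal data with the planned mean and SD and 100 per arm; the trigger rates also assume a mechanical Shapiro-Wilk test.

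**What to change.** - State in SAP 12.5.1 that the untransformed mL-scale model is the sole primary analysis for non-inferiority and superiority, whatever the normality diagnostics show, and fix the method for its 95% confidence interval in advance. The pooled and HC3 intervals performed alike here; what matters is that one is named.
- Delete the switching instructions in SAP 12.5.1.3 and align that section with 12.5.1.4 and 4.1.
- Label the log-scale and rank analyses as sensitivity or descriptive only. Say how a calculated blood loss of zero or below is handled on the log scale, where it is undefined.
- If a rank analysis is to be compared with 150 mL, subtract 150 mL from the BT524 values or report a stratified Hodges-Lehmann interval. State that it targets a location shift, not a mean difference, and that it does not replace the primary analysis.

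The cost is SAP wording and a few lines of code before database lock. No new data are needed.

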12.5.1.4 Alternative Method

The statistical assumptions for the ANOVA model will be tested in regards to the primary endpoint. Primarily the outcome of a Shapiro-Wilk test and graphical quantile-quantile (QQ) plots will used to assess if the

assumptions are significantly violated. If deemed necessary other test may be performed as well. The methods used, and the conclusions will be discussed in the clinical trial report (CTR).

In case there is a significant violation to the assumptions for the ANOVA model for the primary endpoint, a non-parametric alternative method will be implemented, proposed by van Elteren for stratified or blocked continuous response variables.

This alternative method will be used as a sensitivity analysis to the primary non-inferiority analysis for the PPS, FAS and mFAS. It will also be used as a sensitivity to the superiority analysis for the FAS and mFAS.

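### The van Elteren fallback for non-inferiority is given no 150 mL null, interval or decision rule, and the SAP does not fix whether it replaces or only supports the ANOVA.

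*SAP*

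**What the plan says.** SAP 12.5.1 states the primary hypothesis on the difference in mean blood loss, with "δ = non-inferiority margin = 150 mL". The decision rule is an interval: "Non-inferiority will be demonstrated if the upper confidence limit of the 95% confidence interval for the difference in the least square means" is below that margin. Protocol 10.5 has the same rule and no fallback.

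SAP 12.5.1.3 starts with a log transformation if the ANOVA diagnostics fail. If the log-scale model passes, it is the one to be used. Otherwise: "If they do not hold then the alternative method shall be used on the non-log-transformed data".

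SAP 12.5.1.4 says that, on a significant violation, "a non-parametric alternative method will be implemented, proposed by van Elteren for stratified or blocked continuous response variables". It then gives the role: "This alternative method will be used as a sensitivity analysis to the primary non-inferiority analysis for the PPS, FAS and mFAS". The next sentence assigns the same method to superiority in the FAS and mFAS. SAP 4.1 records only that the transformation and the van Elteren method were added to Protocol 10.5.

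Neither 12.5.1.3 nor 12.5.1.4 gives the rank test a null hypothesis, a margin, an estimate with an interval, or a rule for concluding non-inferiority.

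**The concern.** The van Elteren test is a stratified rank-sum test. Unless the data are shifted first, its null is no difference between arms. SAP 12.5.1.1 has that null for superiority, but SAP 12.5.1 has a null at 150 mL. One unmodified method cannot serve both.

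A programmer following 12.5.1.4 literally would produce a p-value against zero and report it beside a non-inferiority claim. Requiring significance in favour of BT524 would turn the check into a superiority test. Treating non-significance as agreement would take absence of evidence for non-inferiority. The SAP prescribes neither reading and rules out neither.

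The second issue is which analysis decides. Section 12.5.1.3 reads as replacement and 12.5.1.4 as sensitivity. Section 12.5.1 leaves transformation and alternatives to discussion at the blind data review meeting. The log-scale ANOVA has a similar gap: it can become the analysis used, yet no margin is given on the log scale.

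**Working it through.** **Inputs (SAP 6.2).** The SAP takes "a standard deviation (SD) of 375 mL, a non-inferiority margin of 150 mL". The control-arm mean is put at about 500 mL, alpha is 2.5% one-sided, power is 80%, and the target is 100 evaluable per arm. The true difference under the alternative is not given; 0 mL is assumed.

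**The plan's own figure.** n per arm = 2 × (1.960 + 0.842)² × 375² / 150² = 2 × 7.85 × 6.25 = 98.1, so 99. The noncentral t gives 79.97% power at 99 and 80.4% at 100. The stated 100 per arm reproduces.

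**Will the fallback be reached?** At mean 500 and SD 375 a normal distribution would put Φ(−500/375) = Φ(−1.33), about 9%, below zero, which is impossible for blood loss. The raw data are therefore likely to be skewed. Simulated Shapiro-Wilk at n = 200 rejects in 100% of raw samples, gamma or lognormal. After the log it rejects in about 96% of gamma samples but only 5% to 6% of lognormal ones. Failure on the raw scale is likely; failure after the log depends on a distribution the documents do not give.

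**Zero-null test at the margin, by hand (normal data).** SE of the difference = 375 × √(2/100) = 53.0 mL, and 150/53.0 = 2.83. Rank tests have efficiency 3/π = 0.955 relative to the t-test, so the noncentrality is 2.83 × √0.955 = 2.76. P(non-significant) = Φ(1.96 − 2.76) = Φ(−0.80), about 21%.

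**Simulation.** 4,000 trials per row, 100 per arm, two equal strata with no stratum effect, BT524 a pure location shift of control. Distributions and strata are assumptions.

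| True shift | Data | Unshifted: favours BT524 | Unshifted: non-significant | Unshifted: against BT524 | Shifted by 150 mL: shows NI | t interval: shows NI |
|---|---|---|---|---|---|---|
| 0 | normal | 2.5% | 94.5% | 3.0% | 77.0% | 79.1% |
| 0 | lognormal | 2.5% | 95.2% | 2.3% | 98.6% | 81.6% |
| +75 | normal | 0.1% | 70.5% | 29.4% | 26.2% | 27.3% |
| +75 | lognormal | 0.0% | 42.7% | 57.3% | 56.9% | 29.7% |
| +150 | normal | 0.0% | 21.3% | 78.7% | 2.4% | 2.4% |
| +150 | lognormal | 0.0% | 1.2% | 98.8% | 1.8% | 2.3% |

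Gamma data at +150 mL give about 7% non-significant with two equal strata. They give about 15% with 80 spine subjects per arm at mean 500 mL and 20 PMP subjects per arm at an assumed 1,500 mL, CV 0.75. The range over these scenarios is about 1% to 21%.

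At +75 mL, inside the margin, the unshifted test is significantly adverse in 29% to 57% of trials. Neither a non-significant nor an adverse result shows on which side of 150 mL the difference lies.

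**Limit of the shifted test.** The margin is on means. If BT524 raises mean loss by 150 mL at constant CV 0.75 (a proportional change), the shifted rank test wrongly shows non-inferiority in about 11% to 16% of skewed-data trials, and in 18% with lognormal data in two equal strata. The mL-scale ANOVA stays at about 2% to 3%.

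**The case against.** Several stronger readings are tempting, and the documents do not support them.

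- **That the SAP tests non-inferiority against zero.** It is silent on the null. Section 12.5.1.4 attaches the method to the non-inferiority analysis, whose hypothesis contains 150 mL, and a margin-shifted run is compatible with that text. The defect is that the shift is unspecified and the standard default is zero.
- **That the fallback can neither support nor challenge non-inferiority.** Under a location shift, significance in favour of BT524 implies a difference below 150 mL and so supports it. This happens in only about 2.5% of trials at a true difference of zero.
- **That the plan has a false non-inferiority rate of about 15%.** This needs a rule that the SAP does not contain (non-significance counts as non-inferiority) together with assumed strata. The 80/20 layout has a pooled mean of 0.8 × 500 + 0.2 × 1,500 = 700 mL, which does not match the planned 500 mL.
- **That the primary conclusion will probably rest on this test.** The log-scale ANOVA comes first and would usually pass with lognormal data. Shapiro-Wilk is not an automatic switch, because plots and a blind review also count. Section 12.5.1.4 calls the method a sensitivity analysis, and 12.5.2 ties superiority to the primary analysis.

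A fair objection to the remedy also stands: a shifted rank test or Hodges-Lehmann interval targets a location shift, not a difference in means. It can only be supportive.

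What remains is the missing margin, estimate and rule, and the conflict between 12.5.1.3 and 12.5.1.4. Neither is answered elsewhere in the SAP or the protocol.

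**Conclusion.** The concern holds as a gap in specification with a misleading default. As written, the van Elteren analysis is not tied to the 150 mL hypothesis, and the SAP does not fix which analysis decides non-inferiority once diagnostics fail. The 1% to 21% range at a +150 mL shift rests on assumed distributions and strata; it shows why non-significance must not be read as support and is not an error rate of the plan. The likely failure of the raw-scale normality check follows from the SAP's own mean and SD under skewed, non-negative data. Whether the log step also fails is unknown. The correction should be made before database lock.

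**What to change.** 1. In SAP 12.5.1.3 and 12.5.1.4, state that the mL-scale ANOVA interval compared with 150 mL remains the deciding analysis whatever the diagnostics show, and that the log-scale ANOVA and the van Elteren method are both supportive only. Removing the mandatory wording about the rank test alone is not enough, because 12.5.1.3 would still let the log-scale model take over.
2. In 12.5.1.4, for non-inferiority, state the null as a shift of at least 150 mL. Run van Elteren on BT524 values minus 150 mL, one-sided at 2.5%, and report a stratified Hodges-Lehmann shift estimate with its 95% interval against 150 mL.
3. Use the unshifted test only for superiority.
4. Add the caveat that the shifted test addresses a location shift, and that its error at a 150 mL mean difference can reach the levels shown above if the difference is proportional.

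The cost is a few lines of SAP text and SAS code, with no new data. The downside is that the supportive result may differ from the ANOVA when the arms differ by more than a shift, and the report must then explain this.
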